Grade 4: Life-threatening consequences; urgent intervention indicated	
confirmation biopsy with lower GI endoscopy.
 
 • In addition to symptomatic treatment (diet, hydration, loperamide, antibiotics if indicated); initiate immediate treatment with intravenous steroids (methylprednisolone 1mg/kg/day) followed by high dose oral steroids (1 to 2 mg/kg/day prednisone equivalents) • When symptoms improve to ≤ Grade 1, steroid taper should be started and continued over no less than 4 weeks as per Section 6.5.1.3.1. • Taper over 6 to 8 weeks in subjects with diffuse and severe ulceration and/or bleeding. • If no improvement in 2-3 days: consider initiating infliximab 5 mg/kg and continue steroids. (Infliximab is contraindicated in subjects with sepsis or a perforation). Upon symptomatic relief initiate a prolonged steroid taper over 45 to 60 days. • If symptoms worsen during steroid reduction, initiate a re-tapering of steroids starting at a higher dose followed by a more prolonged taper and administer infliximab. • If symptoms persist despite the above treatment, a surgical consult should be obtained. 	
5 Re-escalation of the subject's dose is recommended if criteria in Section 6.5.1.2 are met.
 
 • AE resolution to ≤ Grade 1 or baseline must occur within a period of 4weeks since a grade 3 event has been identified 
2nd occurrence
 
 • Interrupt dabrafenib and trametinib until ≤ Grade 1, and then reduce dabrafenib and trametinib to the next lower dose per Table 6-5. Re-escalation of the subject's dose is recommended if criteria in Section 6.5.1.2 are met. 
3rd occurrence
 
 • Permanently discontinue dabrafenib and trametinib.
	Same as Grade 3	Permanently discontinue, dabrafenib and trametinib.

6.5.1.3.14 Mandatory dose modification and management guideline for new malignancies suspected to be related to dabrafenib and/or trametinib treatment

New cutaneous malignancies:

Cutaneous squamous cell carcinoma (CuSCC), keratoacanthomas (KA) and new primary melanomas have been observed in patients treated with dabrafenib and dabrafenib/trametinib combination therapy. These treatment-related lesions should be surgically removed according to institutional practices. Dose modification or interruption of study treatment is not required for cuSCC, KA, or new primary melanoma. However, cuSCC and new primary melanoma should be reported as a SAE. In addition, a biopsy of the lesion should be taken, where possible, and submitted for further analyses and a summary of the results submitted to Novartis.

Subjects should be instructed to immediately inform their physician if new lesions develop. Skin examination should be performed prior to initiation of study treatment and throughout therapy as detailed in the Visit Evaluation Schedule. Monitoring should follow institutional

guidelines and/or as clinically indicated following discontinuation of dabrafenib or until initiation of another anti-neoplastic therapy.

New non-cutaneous malignancies:

In vitro experiments have demonstrated paradoxical activation of MAP-kinase signaling in *BRAF* wild-type cells with RAS mutations when exposed to *BRAF* inhibitors, which may lead to increased risk of non-cutaneous malignancies in patients treated with dabrafenib. Cases of RAS-driven malignancies have been seen with *BRAF* inhibitors, including dabrafenib. Subjects should be monitored as clinically appropriate. Consider the benefits and risks before continuing treatment with dabrafenib in subjects with a non-cutaneous malignancy harboring a RAS mutation. No dose modification of trametinib is required when taken in combination with dabrafenib.

Following discontinuation of dabrafenib, monitoring for non-cutaneous secondary/recurrent malignancies should continue for up to 6 months or until initiation of another anti-neoplastic therapy.

New cutaneous and non-cutaneous malignancies that are reported to the Investigator should be reported as an SAE. A biopsy of the new malignancy should be taken, where possible, and submitted for further analyses including RAS mutation status. Testing of these biopsies may include analysis of genomic alterations, which include but not limited to DNA, RNA and protein analysis of these biopsy specimens, and would analyze the biological pathways known to be associated with, and relevant to, *BRAF*-mutant tumor activation.

6.5.1.3.15 Mandatory dose modification and management guideline for visual changes suspected to be related to dabrafenib and/or trametinib treatment

Episodes of visual changes have been observed in patients receiving trametinib, dabrafenib or the combination of dabrafenib/trametinib. An ophthalmologist should be consulted if changes in vision develop. If a subject reports loss of vision or other visual disturbances, an urgent ophthalmological evaluation (within 24 hours) is recommended to detect potential retinal vein occlusion (RVO). However, if the visual changes are clearly unrelated to study treatment (e.g., allergic conjunctivitis), then monitor closely as it may be reasonable to defer ophthalmic examination.

Treatment with dabrafenib has been associated with the development of uveitis, including iritis. Monitor subjects for visual signs and symptoms (such as, change in vision, photophobia and eye pain) during therapy. Permanently discontinue dabrafenib for persistent \geq Grade 2 uveitis (including iritis and iridocyclitis) of $>$ 6 weeks duration. No dose modification of trametinib is required when taken in combination with dabrafenib.

In subjects treated with trametinib, special attention should be given to retinal findings (e.g., RPED) or retinovascular abnormalities (i.e., branch or central RVO). Treatment-emergent cases of RVO and RPED should be reported as SAEs.

Guidelines for dose modification and management for visual changes and/or ophthalmic examination findings considered to be related to dabrafenib and/or trametinib are provided in [Table 6-18](#) and [Table 6-19](#).

Table 6-18 Mandatory dose modification and recommended clinical management for visual changes and/or ophthalmic examination findings suspected to be related to dabrafenib and/or trametinib treatment

Visual changes (Eye disorders – Other, CTCAE Version 4.03)		
Grade	Recommended adverse event management guidelines	Mandatory dose modification requirements
Grade 1 ^a	
 Consult ophthalmologist within 7 days of onset 	
 If dilated fundus examination cannot be performed within 7 days of onset, interrupt trametinib until RPED and RVO can be excluded by retina specialist/ophthalmologist. Continue dabrafenib. If RPED and RVO excluded, continue (or restart) trametinib at the same dose level. If RPED suspected or diagnosed: see RPED dose modification in Table 6-19; report as SAE if diagnosed. If RVO diagnosed: Permanently discontinue trametinib and report as SAE.
Grade 2 and Grade 3	
 Consult ophthalmologist immediately, perform ophthalmological evaluation within 24 hours. 	
 Interrupt trametinib. Dabrafenib may be continued at the same dose ^b. If RPED and RVO excluded, restart trametinib at the same dose level. If RPED diagnosed, see RPED dose modification in Table 6-19; report as SAE. If RVO diagnosed: Permanently discontinue trametinib and report as SAE.
Grade 4	
 Consult ophthalmologist immediately, perform ophthalmological evaluation within 24 hours. 	
 Interrupt trametinib. Dabrafenib may be continued at the same dose ^b. If RPED and RVO excluded, should consider restarting trametinib at same or reduced dose after discussion with study medical monitor. If RVO or RPED diagnosed, permanently discontinue trametinib and report as SAE.

^a. If visual changes are clearly unrelated to study treatment (e.g., allergic conjunctivitis), monitor closely but ophthalmic examination is not required.

^b. Permanently discontinue dabrafenib for ≥ Grade 2 uveitis (including iritis and iridocyclitis) of > 6 weeks duration.

Table 6-19 Mandatory dose modification and recommended clinical management for retinal pigment epithelial detachments (RPED) suspected to be related to trametinib treatment

Retinal pigment epithelial detachments (RPED) CTCAE Version 4.03		
Grade	Recommended adverse event management guidelines	Mandatory dose modification requirements

 Grade 1 (Asymptomatic; clinical or diagnostic observations only) 	
 If RPED worsens follow instructions below. 	
 Continue treatment with retinal evaluation monthly until resolution.

 Grade 2-3 RPED (Symptomatic with mild to moderate decrease in visual acuity). 	
 Retinal evaluation monthly. 	
 Interrupt trametinib for up to 3 weeks. If improved to ≤ Grade 1, restart trametinib at a lower dose per Table 6-5. If not improved to ≤ Grade 1 within 3 weeks, permanently discontinue trametinib

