6.5.1.2 Other dose modifications and reductions

The following sections address the specific instructions for mandatory dose modifications and recommended management for AEs considered suspected to be related to study treatment. For subjects who do not tolerate the protocol-specified dosing schedule, dose interruptions or modifications are mandated in order to allow subjects to continue study treatment.

Three dose reductions for dabrafenib and two dose reductions for trametinib are permitted. If more dose reductions of dabrafenib and trametinib are required, the subject must be permanently discontinued from that specific study treatment. Dose modification steps for dabrafenib and trametinib in [Table 6-5](#) must be followed for the AEs presented in [Section 6.5.1](#).

Table 6-6 provides sections where detailed dose modification and management requirements for relevant AEs can be found. All AEs are to be graded according to NCI-CTCAE v4.03, unless otherwise specified. Investigators should refer to the current dabrafenib and trametinib local prescribing information for additional information regarding the background of each drug and the management of other AEs or potential safety-related issues not specifically mentioned in this protocol.

If treatment-related toxicities occur that are specific to combination treatment of dabrafenib and trametinib, then both treatments should be simultaneously dose reduced, interrupted or discontinued with the exceptions shown below:

Exception where dose modification is necessary for **only dabrafenib**:

- Uveitis (Table 6-18)

Exception where dose modifications are necessary for **only trametinib**:

- RVO (Table 6-18) and retinal pigment epithelial detachment (RPED) (Table 6-19)
- Left ventricular ejection fraction (LVEF) reduction (Table 6-15)

If a subject's dose of dabrafenib and trametinib has been reduced per the dose modification instructions, re-escalation of the subject's dose is recommended provided the following criteria are met:

- a period of 4 weeks of treatment has passed since restarting dosing at the lower dose level and there is no recurrence of the AE
- the subject is deriving clinical benefit

For dabrafenib and/or trametinib related adverse events: if following an interruption of dabrafenib and trametinib, an AE doesn't recover to \leq Grade 1 or baseline within 4 weeks, dabrafenib and trametinib must be discontinued.

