Grade 3: Severe symptoms; limits self-care ADLs; oxygen indicated	
 • CT scan (high-resolution with lung windows) • Clinical evaluation and laboratory work-up for infection • Consult pulmonologist • Pulmonary function tests-if < normal, repeat every 8 weeks until \geq normal • Bronchoscopy with biopsy and/or BAL if possible • Treat with intravenous steroids (methylprednisolone 125 mg) as indicated. When symptoms improve to \leq Grade 1, a high dose oral steroid (prednisone 1 to 2 mg/kg once per day or dexamethasone 4 mg every 4 hours). • If IV steroids followed by high dose oral steroids does not reduce initial symptoms within 48 to 72 hours, consider non-corticosteroid immunosuppressive medication (e.g., infliximab, cyclophosphamide, IVIG or mycophenolate mofetil). 	
 • Interrupt trametinib until recovery to Grade \leq1 or baseline. Dabrafenib may continue. • Once recovered, trametinib may be restarted at the next lower dose per Table 6-5. Re-escalation of the subject's dose is recommended if criteria in Section 6.5.1.2 are met • If no recovery to Grade \leq 1 or baseline within 4 weeks, permanently discontinue trametinib. Dabrafenib may continue.
Grade 4: Life-threatening respiratory compromise	Same as Grade 3	Same as Grade 3

6.5.1.3.7 Dose modification and management guideline for adverse events suspected to be related to dabrafenib and/or trametinib (other than Pyrexia)

For adverse events of special interest reported **only for dabrafenib and/or trametinib**, general guidelines for dose modification in [Table 6-11](#) should be followed for dabrafenib and trametinib.

In general, if an AE resolves to Grade 1 or baseline at the reduced dose level, and no additional toxicities are seen after 4 weeks of study treatment at the reduced dose, the dose may be increased to the previous dose level.

A dose reduction below 50 mg BID for dabrafenib or below 1 mg QD for trametinib is not allowed. If a dose reduction below 50 mg BID for dabrafenib is required, dabrafenib will be permanently discontinued but these subjects will be allowed to continue trametinib. If a dose reduction below 1.0 mg QD for trametinib is required, then trametinib will be permanently discontinued, but these subjects will be allowed to continue dabrafenib.

Table 6-11 General guidelines for dose modification for adverse events suspected to be related to dabrafenib and/or trametinib treatment

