Grade	Recommended adverse event management guidelines	Mandatory dose modification requirements
Grade 1 or Grade 2 tolerable	
 • Monitor closely. • Provide supportive care according to institutional standards. 	
 • Continue dabrafenib and trametinib at the same dose level.
Grade 2 (intolerable) or Grade 3	
 • Monitor closely. • Provide supportive care according to institutional standards. 	
 • Interrupt dabrafenib and trametinib (except for cuSCC, keratoacanthoma, new primary melanoma, and basal cell carcinoma) • When toxicity resolves to ≤ Grade 1 or baseline, restart dabrafenib and trametinib reduced by one dose level per Table 6-5. Re-escalation of the subject's dose is recommended if criteria in Section 6.5.1.2 are met • If the Grade 2 (intolerable) or Grade 3 toxicity recurs, interrupt dabrafenib and trametinib. • When toxicity resolves to Grade 1 or baseline, restart dabrafenib and trametinib reduced by another dose level per Table 6-5. Re-escalation of the subject's dose is recommended if criteria in Section 6.5.1.2 are met

Grade	Recommended adverse event management guidelines	Mandatory dose modification requirements
Grade 4	
 • Monitor closely. • Provide supportive care according to institutional standards. 	
 • Interrupt dabrafenib and trametinib. • Restart with dabrafenib and trametinib reduced by one dose level per Table 6-5 once toxicity resolves to \leq Grade 1 or baseline or permanently discontinue dabrafenib and trametinib at the discretion of the investigator. Re-escalation of the subject's dose is recommended if criteria in Section 6.5.1.2 are met

6.5.1.3.8 Mandatory dose modifications and recommended clinical management guidelines for hand-foot reaction (palmar-plantar erythrodysesthesia)

In general, management of hand-foot skin reactions include:

- Prevention/prophylaxis: promote sunscreen use and avoidance of unnecessary sun exposure, use alcohol-free emollient creams, topical steroids and antibiotics as needed.
- Pruritic lesions: cool compresses and oral antihistamines
- Fissuring lesions: Monsel's solution, silver nitrate or zinc oxide cream
- Desquamation: thick emollients and mild soap
- Paronychia: antiseptic bath, local potent corticosteroids, antibiotics, surgery as needed
- Infected lesions: topical or systemic antibiotics

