Grade 3 with clinically significant bleeding Grade 4	
 Grade 3: monitoring blood test more frequently (every 3-5 days) 	
1st occurrence:
 
 Interrupt dabrafenib and trametinib until toxicity resolves to ≤ Grade 2 or baseline. Restart dabrafenib and trametinib at same dose. 
2nd occurrence:
 
 Interrupt dabrafenib and trametinib until toxicity resolves to ≤ Grade 2 or baseline. Restart dabrafenib and trametinib at the next lower dose per Table 6-5. Re-escalation of the subject's dose is recommended if criteria in Section 6.5.1.2 are met 
3rd occurrence:
 
 Interrupt dabrafenib and trametinib until toxicity resolves to ≤ Grade 2 or baseline. Restart dabrafenib and trametinib at another lower dose per Table 6-5. Re-escalation of the subject's dose is recommended if criteria in Section 6.5.1.2 are met 
4th occurrence:
 
 Interrupt dabrafenib and trametinib until toxicity resolves to ≤ Grade 2 or baseline. Permanently discontinue dabrafenib and trametinib.

6.5.1.3.10 Mandatory dose modifications and recommended clinical management guidelines for non-hematological adverse events

Guidelines for dose modification for non-hematologic adverse events suspected to be related to study treatment by the investigator are provided in [Table 6-14](#).

Table 6-14 Mandatory dose modifications and recommended clinical management guidelines for non-hematological adverse events

Non-Hematologic AEs (except Grade 2 alopecia, Grade 2 fatigue) (NCI-CTCAE v4.03)		
Grade	Recommended adverse event management guidelines	Mandatory dose modification requirements
Grade 1-2 tolerable	
 Monitor closely. Provide supportive care according to institutional standards. 	
 Continue, dabrafenib and trametinib at the same dose.

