Grade 2 intolerable or Grade 3	
 Monitor closely Provide supportive care according to institutional standards 	
1st or 2nd occurrence:
 
 Interrupt dabrafenib and trametinib until toxicity recovers to ≤ Grade 1 or baseline. Restart dabrafenib and trametinib at the same dose. 
3rd occurrence:
 
 Restart dabrafenib and trametinib at the next lower dose per Table 6-5. Re-escalation of the subject's dose is recommended if criteria in Section 6.5.1.2 are met 
4th occurrence:
 
 Permanently discontinue dabrafenib and trametinib.
Grade 4	
Monitor closely
 
Provide supportive care according to institutional standards
	
1st occurrence:
 
 Interrupt dabrafenib and trametinib. Dabrafenib and trametinib may be reinitiated at the next lower dose per Table 6-5. Re-escalation of the subject's dose is recommended if criteria in Section 6.5.1.2 are met 
2nd occurrence:
 
 Permanently discontinue dabrafenib and trametinib.

6.5.1.3.11 Mandatory dose modification and management guideline for changes in LVEF suspected to be related to dabrafenib and/or trametinib treatment

Decreases of left-ventricular-ejection-fraction (LVEF) have been observed in patients receiving trametinib in combination with dabrafenib. Therefore, ECHOs must be performed to assess cardiac ejection fraction in regular intervals as outlined in the Visit Evaluation Schedule ([Table 8-1](#)). Dose modification guidance and stopping criteria for LVEF decrease are provided in [Table 6-15](#).

Table 6-15 Mandatory dose modification and recommended clinical management for changes in LVEF suspected to be related to dabrafenib and/or trametinib treatment

Left Ventricular Ejection Fraction decrease (NCI-CTCAE v4.03)		
LVEF-drop (%) & clinical symptoms	Recommended adverse event management guidelines	Mandatory dose modification requirements

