6.5.1.3.16 Monitoring guideline for hyperglycemia suspected to be related to dabrafenib treatment

Hyperglycemia requiring an increase in the dose of, or initiation of insulin or oral therapy can occur with dabrafenib. Monitor serum glucose levels as clinically appropriate during treatment with dabrafenib in subjects with pre-existing diabetes or hyperglycemia.

Advise subjects to report symptoms of severe hyperglycemia such as excessive thirst or any increase in the volume or frequency of urination.

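### Tables 6-11 and 6-14 give different mandatory restart doses for related pancreatitis or hypersensitivity after a recovered intolerable Grade 2 or Grade 3 event

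*Protocol*

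**What the plan says.** Section 6.5.1.3.7 has a routing sentence. It begins "For adverse events of special interest reported", limits itself to events reported for one or both study drugs, and sends them to Table 6-11. For an intolerable Grade 2 or a Grade 3 event, the mandatory column of that table interrupts both drugs. When toxicity has fallen to Grade 1 "or baseline, restart dabrafenib and trametinib reduced by one dose level per Table 6-5". On recurrence it interrupts again and takes both drugs down a further level.

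Section 6.5.1.3.10 has a scope sentence of its own: "Guidelines for dose modification for non-hematologic adverse events suspected to be related to study treatment by the investigator are provided in" Table 6-14. The header of that table reads "Non-Hematologic AEs (except Grade 2 alopecia, Grade 2 fatigue) (NCI-CTCAE v4.03"; those two exceptions are the only ones. For the same grades, its mandatory column interrupts both drugs until recovery and then, after a first or second occurrence, says "Restart dabrafenib and trametinib at the same dose". The next lower dose comes only after the third occurrence.

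Table 10-1 lists pancreatitis and hypersensitivity as AESIs. Neither has a row in Table 6-6, the index of toxicity rules. That index lists non-hematologic events (Table 6-14) and *General* (Table 6-11) as separate rows and does not rank them.

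**The concern.** A related pancreatitis or hypersensitivity event is both an AESI and a non-hematologic event, so on their wording both tables apply. Both dose columns are headed as mandatory, and a site cannot restart one level lower and at the same dose.

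Two things are at stake. The first is conduct: after a severe drug-related toxicity that has recovered, one table lowers the exposure and the other returns the subject to the dose that preceded the event, and does so again after a second event. The second is record-keeping: a site that follows one column can be written up as deviating from the other. SAP 5.3.1 tabulates and lists all protocol deviations, and SAP 5.4.1 summarises dose reductions.

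**Working it through.** The plan gives no figure on this point, so there is none to reproduce. The check compares the scope of the two tables and then traces the dose under each.

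**Scope**

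1. Is the event an AESI? Yes for both: Table 10-1 lists pancreatitis for dabrafenib and the combination, and hypersensitivity for each drug and the combination. Section 6.5.1.3.7 therefore leads to Table 6-11.
2. Is it non-hematologic and suspected to be related? Yes, by assumption of the case. Section 6.5.1.3.10 therefore leads to Table 6-14, and neither exception in its header applies.
3. Is there a more specific rule? No. Table 6-6 has no row for either event and section 6.5.1.3 has no section for either. Section 6.5.1.1 mentions hypersensitivity only as part of the fever work-up.
4. Does any other text rank the tables? Section 6.5.1.2 refers to the local label for events the protocol does not specifically mention. It does not rank Table 6-11 against Table 6-14.

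**Dose after a first recovered event**

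The steps come from Table 6-5: dabrafenib 150 then 100 mg BID (300 then 200 mg/day), and trametinib 2 then 1.5 mg QD. The subject is at full dose when the event occurs.

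| | Table 6-11 | Table 6-14 | Ratio |
|---|---|---|---|
| Dabrafenib, mg/day | 200 | 300 | 200/300 = 67% |
| Trametinib, mg/day | 1.5 | 2 | 1.5/2 = 75% |

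**Cost in relative dose intensity (RDI)**

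Table 6-11 recommends re-escalation when the criteria in section 6.5.1.2 are met: 4 weeks of treatment at the lower level without recurrence, and clinical benefit. SAP 5.4.1 defines RDI as dose intensity over planned dose intensity, which for one subject equals actual over planned cumulative dose. Section 3 sets a study month at 28 days, so 12 months is 12 × 28 = 336 days. The interruption is the same under both tables and cancels.

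RDI difference per event = 28 × (fraction of dose withheld) / 336.

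- Dabrafenib: withheld fraction 100/300 = 1/3, so 28 × (1/3) / 336 = 0.028, or 2.8 points.
- Trametinib: withheld fraction 0.5/2 = 0.25, so 28 × 0.25 / 336 = 0.021, or 2.1 points.

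**The case against.** The strongest answer is that section 6.5.1.3.7 already settles the matter. It names AESIs and sends them to Table 6-11, while Table 6-14 speaks of non-hematologic events at large, so the specific text prevails. This is the better reading, and it would be too strong to say that the protocol offers no guidance. It is not the only reading, however. The title of Table 6-11 covers any event suspected to be related, Table 6-6 labels it *General*, and the header of Table 6-14 lists its exceptions without AESIs. A site could apply the same specific-over-general principle and land on Table 6-14.

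It can also be said that other rules limit the harm. That stands. Section 6.5.1.2 stops both drugs if a related event has not recovered within 4 weeks, and section 9.1.1 obliges the investigator to stop treatment that would harm the subject. Neither rule, though, says at which dose to restart a subject who has recovered and may continue.

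A reader might infer more than the documents support, in three ways:

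- **A Grade 4 conflict.** Table 6-14 stops both drugs at a second Grade 4 event. Table 6-11 allows a reduced restart or lets the site "permanently discontinue dabrafenib and trametinib at the discretion of the investigator". Stopping satisfies both tables, so the rules differ in strictness without contradicting each other.
- **A widening dose gap over later events.** Table 6-11 gives no step for a third event and recommends re-escalation between events. Dose paths that ignore re-escalation or run to a third or fourth event overstate the size.
- **Hyperglycemia as a third case.** It has its own row in Table 6-6 and its own section, which says "Monitor serum glucose levels as clinically appropriate during treatment with dabrafenib in subjects with pre-existing diabetes or hyperglycemia" and gives no dose rule. That gap deserves a separate clarification and is not part of this conflict.

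**Conclusion.** The conflict is real but narrow. It concerns related pancreatitis and hypersensitivity, at intolerable Grade 2 or Grade 3, in subjects who recover and restart. The text leans towards Table 6-11 without making that clear.

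For a subject at full dose, the first restart is dabrafenib 200 against 300 mg/day and trametinib 1.5 against 2 mg. If the dose is re-escalated after 4 weeks, one event is worth about 2.8 and 2.1 RDI points. That rests on a full 336 days of exposure and on re-escalation as soon as the criteria allow.

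The documents do not give the number of subjects affected. It is probably small: neither event is among the most frequent adverse events, overall or at Grade 3/4, that section 1.1.1.6 reports for COMBI-AD. Pyrexia has its own rule in section 6.5.1.1 and Table 6-4, so the primary endpoint is untouched. Severity is minor. It is still worth correcting, because two mandatory instructions for serious drug toxicities cannot both be followed.

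**What to change.** 1. In section 6.5.1.3.10 and the header of Table 6-14, add an exception for AESIs, and say that those without a dose rule of their own follow Table 6-11. Put a matching note in Table 6-6.
2. In Table 6-11, add for these AESIs the permanent stop of both drugs at a second Grade 4 occurrence that Table 6-14 now contains. Without it, the exception in step 1 would remove the only text that requires a stop at that point.
3. Leave the other rows of both tables as they are. Deal with the missing dose rule for hyperglycemia in section 6.5.1.3.16 as a separate item.

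The cost is wording in one protocol amendment and a notice to sites, with no new data or analyses. SAP 5.1 ties the planned primary cut-off of 26 September 2020 to all 556 subjects having completed 12 months of treatment or discontinued. Once treatment has ended, the amendment cannot change dosing in this trial. The useful remainder is then to record that following either table for these two events is not a protocol deviation.
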